4.5.1.2 Treatment Duration and Duration under Observation Definitions

Treatment duration during the DBT and FU1 phases will be calculated as follows:

(Date of the last recorded treatment observation during the DBT and FU1 phases* – Date of first dose of the DBT phase) + 1

*The date of the last recorded treatment observation during the DBT and FU1 phases is defined as the earliest between:

- date of last dose received during the DBT phase + 24 weeks
- last day prior to entering in FU2 as per the subject disposition eCRF page
- last day prior to the first OLE dose
- last day prior to the first PDP OCR dose
- last day prior to start of commercial ocrelizumab treatment or other MS DMT
- clinical cutoff date (CCOD) for the primary analysis reporting
- date of discontinuation from the study as indicated on the subject disposition eCRF page
- date of death

Treatment duration for all ocrelizumab exposed patients will be calculated as follows:

(Date of the last recorded treatment observation for all ocrelizumab exposed patients*–Date of the first dose of ocrelizumab (study drug, PDP OCR, OLE OCR or commercial ocrelizumab))+ 1

*The date of the last recorded treatment observation for all ocrelizumab exposed patients is defined as the earliest between:

- date of last dose of ocrelizumab (study drug, PDP OCR, OLE OCR or commercial ocrelizumab)+24 weeks
- last day prior to start of other MS DMT (not including commercial ocrelizumab)
- date of discontinuation from the study as indicated on the subject disposition eCRF page
- CCOD for the primary analysis reporting
- date of death

The duration under observation during the DBT and FU1 phases for a patient will be calculated as follows:

(Date of last observation during the DBT and FU1 phases*–Date of first infusion in the first dose)+ 1

*Date of last observation during the DBT and FU1 phases is defined as the earliest between:

- the latest recorded date in all CRF and non CRF data prior to CCOD
- last day prior to entering in FU2 as per the subject disposition eCRF page
- last day prior to the first OLE dose
- last day prior to the first PDP OCR dose
- last day prior to start of commercial ocrelizumab treatment or other MS DMT
- date of discontinuation from the study as indicated on the subject disposition eCRF page
- date of death

The duration under observation for all ocrelizumab exposed patients will be calculated as follows:

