(Date of last observation for all ocrelizumab exposed patients* –Date of first infusion in the first dose of ocrelizumab)+ 1

*Date of last observation for all ocrelizumab exposed patients is defined as the earliest between:

- the latest recorded date in all CRF and non CRF data prior to CCOD

- last day prior to start of other MS DMT (not including commercial ocrelizumab)
- date of discontinuation from the study as indicated on the subject disposition eCRF page
- date of death

The duration of observation, within a dose, is defined in a similar manner as follows:

$(\text{Day prior to first infusion in the } n+1\text{th dose}^* - \text{Date of first infusion in the } n\text{th dose}) + 1$

*With the exception of the last dose received by the patient where the date of last observation during the DBT and FU1 phases or for all ocrelizumab exposed patients is used as defined above.

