4.5.2 Adverse Events

AEs will be defined as all AEs including infusion-related reaction (IRRs) and serious MS relapses, but excluding non-serious MS relapses. Therefore, those AEs recorded on the AE and IRR CRF pages will be included.

For each recorded AE, the term entered by the investigator describing the event (the “reported term”) will be assigned to a standardized term (the “Preferred Term” [PT]) and assigned to a superclass term on the basis of the MedDRA World Health Organization (WHO) dictionary of terms. All analyses of AE data will be performed using the PTs unless otherwise specified.

For all summary tables, the AEs will be sorted by System Organ Class ([SOC]; in decreasing order of overall incidence) and then by PT (in decreasing order of overall incidence). Summaries of AEs will be generated to summarize the incidence of treatment-emergent AEs only. Treatment-emergent events are defined as those AEs with an observed or imputed date of onset on or after the start date of trial treatment or with CRF flag “Event occurred prior to first study drug administration” equals “no”. If the onset date of the AE is prior to the day of first dose, the AE will be considered treatment-emergent only if the most extreme intensity is greater than the initial intensity (i.e., the intensity for a given AE increases and its end date is on or after the date of the first dose). An AE with a completely missing, non-imputed start date will be assumed to be treatment emergent unless the AE has a complete, non-imputed end date that is prior to the date of the first dose.

AEs will be assigned to a dose if the AE onset date is on or after the date of the first infusion of that dose but before the first infusion of the next treatment dose. AEs that are reported during non-dosing phases (Follow-up 1, Follow-up 2) will be assigned to the last dose received. AEs that start prior to the first dose and worsen during treatment (i.e., treatment-emergent) will be assigned to the first treatment dose.

The number of patients who experienced a related AE will be summarized by SOC and PT. AEs will be summarized by SOC and PT by intensity grade. Multiple occurrences of the same event within a patient will be counted once at the greatest intensity/highest grade for this PT. For AEs leading to death, the most extreme intensity will be overwritten by Grade 5 (death). Any AEs and the SOC overall rows of the summary table will count patients according to AEs by intensity (grade).

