All patient deaths will be listed.

SAEs will be defined as all SAEs including serious MS relapses and serious IRRs. The number of patients who experienced an SAE will be summarized by SOC and PT. Related SAEs will be summarized by SOC and PT. Additionally, the most frequent SAEs ($\geq 1\%$) will be presented by SOC and PT.

Clinical relapse will be considered an SAE when the relapse results in hospitalization for any reason other than routine treatment of the relapse (e.g., for a treatment course beyond the standard treatment described or when hospitalization is prolonged). These events will be listed and summarized.

A patient may experience an AE that leads to withdrawal from study treatment. Withdrawal from study treatment for an AE may not necessarily lead to withdrawal from the study. Only AEs that led to study treatment withdrawal are of interest. Patients who withdraw early from the study because of AEs will be summarized under disposition. The number of patients who experienced an AE that led to study treatment withdrawal as well as the number of patients who experienced an AE that led to modification or interruption of study drug will be summarized by SOC and PT. The number of patients previously treated with an another DMT for MS who experienced an AE will be summarized by SOC and PT.

For each treatment group, the incidence count for each AE PT will be defined as the number of patients reporting at least one treatment-emergent occurrence of the event. The incidence rate will be calculated as the incidence count divided by the total number of patients in the population. Each table will also present the overall number of patients experiencing at least one AE and the total number of AEs reported.

The rate per 100 patient-years by treatment group (along with the 95% CI) will be calculated for specific events of interest such as all AEs, SAEs, infections and serious infections (see Section 4.5.4), opportunistic infections ([OIs]; see Section 4.5.5), and malignancies (see Section 4.5.6).

- The number of AEs per 100 patient-years is calculated as:
 $(\text{Total number of AEs} \div \text{Total number of patient-years}) \times 100$

- The 95% confidence interval (CI) for the number of AEs per 100 patient-years will be calculated using the exact method based on the Poisson distribution (Sahai and Khurshid 1993):

Exact lower 95% confidence limit = $\text{chisq}(p = 0.025, df = 2Y) / (2T)$

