Exact upper 95% confidence limit = $\text{chisq}[p = 0.975, df = 2(Y + 1)] / (2T)$

where Y is the total number of AEs, T is total number of patient-years at risk and $\text{chisq}(p, df)$ is the quantile of the upper tail probability of the Chi-squared distribution with df degrees of freedom. This approach has the advantage of providing an estimate for the upper 95% confidence limit even when the total number of AEs is zero.

The rates per 100 patient-years will be summarized by treatment and dose and by treatment (including all doses).

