4.5.4 Infections

Infections will be defined from the AE data using the MedDRA SOC of “Infections and infestations”. Infections will be classified according to the pathogen type (e.g., bacterial, fungal, viral, parasitological, unknown, or other).

An infection will be defined as serious if the event is an SAE as defined in Section 4.5.2. A listing will be presented of non-serious infections treated with an IV anti-infective.

The number of patients who experienced an infection will be summarized by SOC and PT and by intensity.

The number of infections experienced by more than 5% of patients will be summarized by SOC and PT.

The number of patients who experienced a serious infection will be summarized by SOC and PT.

Identified pathogen codes will not be summarized but will only be listed within the listings of infections and serious infections. Infections and serious infections will be summarized by pathogen types.

The rate per 100 patient-years by treatment group (along with the 95% CI) will be calculated for infections and serious infections overall and by dose based on the number of patient-years observation for the specific dose.

For infections and serious infections, the incidence rate ratio will be calculated. For these analyses, the incidence rate ratio with 95% CI based on the Poisson distribution exact method will be presented.

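### Safety rates per 100 patient-years: Poisson limits too narrow for frequent repeat events, the chi-square tail misdefined, and Follow-Up 2 events counted without matching person-time

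*SAP*

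**What the plan says.** **Rates and limits.** SAP 4.5.2 takes the total number of AEs over total patient-years, times 100. The 95% limits are "calculated using the exact method based on the Poisson distribution": chisq(0.025, 2Y)/(2T) below and chisq(0.975, 2(Y+1))/(2T) above, where Y is the event total and T the patient-years. The function chisq(p, df) "is the quantile of the upper tail probability of the Chi-squared distribution with df degrees of freedom". The SAP recommends the method for the zero-event case: "This approach has the advantage of providing an estimate for the upper 95% confidence limit even when the total number of AEs is zero". Rates are given by arm, and by arm and dose. For infections and serious infections, SAP 4.5.4 adds that "the incidence rate ratio with 95% CI based on the Poisson distribution exact method will be presented".

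**What counts as an event.** Protocol 5.3.5.4 records each recurrence as a new event. Protocol 5.3.5.3 has some linked events entered separately; its example of dizziness, a fall and a fracture makes three.

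**Window for events.** SAP 4.5.2: "AEs that are reported during non-dosing phases (Follow-up 1, Follow-up 2) will be assigned to the last dose received". Under SAP 4.5, data in the safety analysis set stop only at PDP OCR, OLE ocrelizumab, commercial ocrelizumab or another MS DMT. Entry to FU2 does not stop them.

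**Window for person-time.** SAP 4.5.1.2 closes each dose on the day before the next one, "With the exception of the last dose received by the patient where the date of last observation during the DBT and FU1 phases" applies. That date is the earliest of several, one of which is the "last day prior to entering in FU2 as per the subject disposition eCRF page". SAP 4.5.4 bases by-dose infection rates on observation time for the specific dose.

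**The concern.** 1. **Width.** An exact Poisson interval on a pooled total is valid only if the total's variance equals its mean. When repeats are counted and patients differ in their underlying rates, the variance is larger and the interval too short. This matters for all AEs and all infections. It matters little for serious infections or malignancies, and not at all for summaries that count patients.
2. **Tail.** The probabilities 0.025 (lower) and 0.975 (upper) suit a lower-tail quantile. Under the upper-tail definition the limits swap, and the zero-event upper limit collapses. Zero events is a realistic case: Protocol 5.1.1.1 reports no opportunistic infections on ocrelizumab in the controlled period of the pivotal MS trials, and SAP 4.5.5 plans that rate by dose.
3. **Person-time.** FU2 events enter the last-dose numerator without FU2 time in its denominator, so the last-dose rate is biased upward.

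These tables are the trial's exposure-adjusted safety output, and the infection rate ratio compares the arms directly.

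**Working it through.** **Nominal level.** Under a pure Poisson count, the printed formula with a lower-tail quantile covers 98.1% at 1 expected event, 97.5% at 10, 95.3% at 50 and 95.0% at 300. The method therefore delivers its stated 95% when its assumption holds. With the upper-tail quantile as defined, coverage was 0% at every mean tried from 0.5 to 3000.

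**Part 1: width.** Give each patient a gamma frailty with mean 1 and variance k (assumed), and let μ be the mean count per patient. Then variance/mean φ = 1 + kμ, and the share with no event is P0 = (1 + kμ)^(−1/k), so φ = P0^(−k). Approximate coverage of a nominal 95% interval is 2Φ(1.96/√φ) − 1. Protocol 1.2 gives any AE in 90.0% (placebo) and 95.1% (ocrelizumab) of patients in the earlier PPMS trial. Protocol 5.1.1.1 gives serious infections in 6.7% and 6.2%.

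| Event | P0 | k | φ | Coverage |
|---|---|---|---|---|
| All AEs, placebo | 0.100 | 0.25 | 1.778 | 85.8% |
| All AEs, placebo | 0.100 | 0.5 | 3.162 | 73.0% |
| All AEs, ocrelizumab | 0.049 | 0.25 | 2.125 | 82.1% |
| All AEs, ocrelizumab | 0.049 | 0.5 | 4.518 | 64.4% |
| Serious infections, placebo | 0.933 | 1 | 1.072 | 94.2% |

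The documents give no figure for all infections. Simulation with 500 patients per arm, equal true rates and 100,000 runs:

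| μ (assumed) | k (assumed) | Rate CI coverage | Rate-ratio CI excludes 1 |
|---|---|---|---|
| 1 | 0.5 | 89.1% | 10.4% |
| 1 | 1 | 83.5% | 15.8% |
| 2 | 0.5 | 83.6% | 16.2% |
| 2 | 1 | 74.6% | 25.6% |
| 0.072 (serious infections) | 1 | 94.8% | 4.6% |

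**Part 2: tail.** Take Y = 20 and T = 400 patient-years (illustrative), so 2T = 800. The limits are multiplied by 100 to match the rate, a factor the printed limits omit.

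- As defined (upper tail): lower = 0.0742, or 7.42 per 100 patient-years; upper = 0.0325, or 3.25.
- Lower tail: 0.0305 and 0.0772, or 3.05 and 7.72.

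The reversal holds for every Y from 1 to 5000 (the range checked). At Y = 0, df = 2 for the upper limit. The upper-tail quantile is 0.0506 and the lower-tail quantile 7.378, a ratio of 145.7. The design assumptions (500 per arm, 144 weeks, 10% annual dropout) give about 1,197 patient-years per arm. Taking T = 1200, the upper limit is 100 × 0.0506/2400 = 0.002 per 100 patient-years as written, against 100 × 7.378/2400 = 0.307.

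**Part 3: person-time.** Consider a patient last dosed at Week d, observed to Week 144 and then through the 24 weeks of FU2 (Protocol 3.1.1.6) before clinical cutoff, with no OLE, PDP OCR, commercial ocrelizumab or other DMT. Last-dose events are counted over 168 − d weeks and person-time over 144 − d weeks.

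| Last dose (week) | Event weeks / person-time weeks | Ratio |
|---|---|---|
| 120 (Dose 6) | 48/24 | 2.0 |
| 96 | 72/48 | 1.5 |
| 72 | 96/72 | 1.33 |
| 48 | 120/96 | 1.25 |

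If a share f of Dose 6 patients is of this kind and events are reported at a constant rate, the Dose 6 rate is inflated by (24 + 24f)/24 = 1 + f: 1.05 at f = 5% and 1.20 at f = 20% (f assumed). If T for the all-dose rate is the DBT/FU1 duration, which the SAP does not state, that rate rises by (144 + 24f)/144: 0.8% and 3.3%.

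Such patients can exist. Protocol 3.1.1.5 sends patients still in FU1 at Week 144 to FU2 and bars them from the OLE, and Protocol 3.2 assumes recruitment over up to 5 years.

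**The case against.** **Tail.** The labels, the probabilities, the degrees of freedom and the cited method all point to the standard exact formula. A programmer would probably use the ordinary quantile, and reversed limits would show in the first table. That is likely for Y of 1 or more, but the definition is still wrong. At Y = 0 no reversal would show: the upper limit would merely be a small positive number.

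**Width.** The intervals are descriptive, crude rates with Poisson limits are the planned method (Protocol 6.5 also uses Poisson limits), and patient-level summaries are provided. The size rests on an assumed frailty variance: taking all-AE rates of 200 to 300 per 100 patient-years and frailty variance 0.5 to 2 instead gives coverage of 37% to 68%. All of this stands as a limit on how exactly the error can be sized. It does not change the direction, since any between-patient variation in rates makes the limits too short.

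**Person-time.** The affected group is narrow. OLE and PDP OCR patients leave the safety-set window first, and patients moved to FU2 at the primary analysis have almost no FU2 time before cutoff. Constant event reporting is doubtful, because infusion reactions count as AEs but cannot arise in FU2, which has no infusions and one scheduled visit. The inflation of all-AE rates is therefore probably below 1 + f. The ocrelizumab exposed set has no FU2 stop and is unaffected, and no effect on the between-arm ratio has been shown. The mismatch between the two rules remains.

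**Conclusion.** The concern holds on all three parts and should be corrected before database lock.

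- The tail definition is wrong as printed and fails in the zero-event case for which the method is recommended.
- In the safety analysis set, the FU2 rule inflates by-dose rates for the last dose, by about the share of patients who complete FU2 before cutoff without further ocrelizumab or another DMT. The overall rate is affected only if T is the DBT/FU1 duration.
- For all AEs, nominal 95% intervals cover about 82% to 86% at frailty variance 0.25 and 64% to 73% at 0.5. For all infections, assuming 1 to 2 events per patient and frailty variance 0.5 to 1, rate coverage is 89% to 75%, and the rate-ratio interval excludes 1 in 10% to 26% of trials with equal true rates, instead of 5%.

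The directions follow from the documents. The frailty variances, the infection rate and the FU2 share are assumptions. No primary, secondary or other inferential result is affected.

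**What to change.** 1. **Frequent repeat events.** For all AEs and all infections, take the rates and the infection rate ratio from a negative binomial model with a log patient-years offset, or from a Poisson model with patient-level robust variance. SAP 4.4.6 already uses negative binomial models with an offset for lesion counts. Keep exact Poisson limits for rare or once-per-patient events.
2. **Quantile.** Change *upper tail* to *lower tail* in the definition of chisq. In the same edit, multiply the limits by 100 to match the rate, and set the lower limit to 0 when Y = 0, where df = 0 leaves it undefined.
3. **Window.** In the safety analysis set, either count only events with onset up to the last-observation date used for the denominator, or extend the denominator through FU2. State which duration T is, and use the same window for by-dose and overall rates.

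The cost is SAP wording and programming; no data collection changes. Intervals for all AEs and all infections will be wider. Stopping the numerator at FU2 removes FU2 events from these rates, while extending the denominator adds off-treatment time. The choice should be recorded before unblinding.

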4.5.3 Infusion Related Reactions

The occurrence of an IRR and its corresponding symptoms are collected on the dedicated eCRF page. Symptoms will be coded in the MedDRA and summarized by PTs.

For IRRs, the number and percentage of patients with at least one infusion reaction will be presented per infusion (patients with multiple events within an infusion will count only once). In addition, the total number of IRRs will be summarized (multiple events will be counted). The total and percentage of events (based on the total number of patients with at least one IRR) by most extreme intensity will be summarized per infusion and per dose. The number of serious IRRs will also be presented. For multiple events in a given patient, the most extreme intensity will be used and the total number of events of each intensity will be equal to the total number of patients with at least one IRR if there are no missing extreme intensities. The total number of IRRs experienced by each subject will be summarized across the treatment doses.

Onset times of IRRs, if known, are recorded on the CRF. The number of patients with at least one IRR, the total number of IRRs, and the intensity of the IRR will be presented by the time of event (i.e., During infusion, Event occurred within 24 hours after end of IMP infusion, time not available) as well as by dose.

Additionally, similar tables will be presented by the pre-medication subgroup (methylprednisolone plus antihistaminics, or methylprednisolone plus antihistaminics and analgesic/antipyretic).

Symptoms of IRRs and symptoms of serious IRRs will be presented by infusion.

Symptoms of IRRs that led to interruption of study drug or symptoms of IRR that led to discontinuation of study drug will also be presented. Symptoms of IRR experienced by Ocrelizumab—F. Hoffmann-La Roche Ltd

Statistical Analysis Plan WA40404

patients during an infusion and symptoms of IRR experienced within 24 hours after end of IMP infusion will also be presented.

In addition, concomitant treatments for IRRs by class and PT will be presented by infusion.

4.5.4 Infections

Infections will be defined from the AE data using the MedDRA SOC of “Infections and infestations”. Infections will be classified according to the pathogen type (e.g., bacterial, fungal, viral, parasitological, unknown, or other).

An infection will be defined as serious if the event is an SAE as defined in Section 4.5.2. A listing will be presented of non-serious infections treated with an IV anti-infective.

The number of patients who experienced an infection will be summarized by SOC and PT and by intensity.

The number of infections experienced by more than 5% of patients will be summarized by SOC and PT.

The number of patients who experienced a serious infection will be summarized by SOC and PT.

Identified pathogen codes will not be summarized but will only be listed within the listings of infections and serious infections. Infections and serious infections will be summarized by pathogen types.

The rate per 100 patient-years by treatment group (along with the 95% CI) will be calculated for infections and serious infections overall and by dose based on the number of patient-years observation for the specific dose.

For infections and serious infections, the incidence rate ratio will be calculated. For these analyses, the incidence rate ratio with 95% CI based on the Poisson distribution exact method will be presented.

4.5.5 Opportunistic Infections

Potential OIs will be retrieved using the "Opportunistic infections (narrow) (Standardised MedDRA Queries [SMQs])" basket.

The number of patients who experienced an OI and serious OI will be summarized by SOC and PT.

The rate per 100 patient-years by treatment group (along with the 95% CI) will be calculated for OIs overall and by dose.

